6.5.1 Treatment at onset of an adverse event

Both onset date and (if requested) onset time of an AE will be compared to the dosing information. Treatment will then be the dose at the last observation for a subject in the dosing file where the AE onset date/time is not earlier than the dose date/time.

6.5.2 Treatment at the time of a laboratory assessment

Laboratory draw date and time will both be compared to the dosing information. Treatment at the time of the laboratory assessment will then be the dose at the last observation for a subject in the dosing file where the laboratory date/time is not earlier than the dose date/time.

6.6 Concomitant medications

Start and stop date of all concomitant medications are collected on the CRF. In order to classify medication as prior, current or concomitant, partial, missing or invalid start and stop dates will be imputed where possible as follows:

- If the reported start date is missing or invalid and the informed consent date is not missing or invalid, then the imputed start date is set equal to the informed consent date. If the consent date is missing or invalid and the birth date is not missing or invalid, then the imputed start date is set equal to the birth date. If the start date, the consent date and the birth date are all invalid or missing, then the imputed start date is set equal to missing.
- If the reported start date is partially entered, then the imputed start date is set equal to the earliest possible reported start date based on the partial entered reported start date.
- If the reported end date is missing, continuing, unknown or invalid, then the imputed end date is set equal to the most recent database extraction date.
- If the reported end date of the medication is partial, then the imputed end date is set equal to the last possible reported end date based on the partial entered reported end date.

Imputed dates will not appear on the listings of non-study medication.

6.7 Counting rules for adverse events

6.7.1 At subject level

Where a subject has the same adverse event, based on preferred terminology, reported multiple times in a single analysis period, the subject will only be counted once at the preferred terminology level in adverse event frequency tables.

Where a subject has multiple adverse events within the same system organ class in a single analysis period, the subject will only be counted once at the system organ class level in adverse event frequency tables.

When a subject has the same adverse event, based on preferred terminology, reported multiple times in a single analysis period, the following criteria, in order of precedence, will be used to select the event to be included in summary tables:

- Relationship to study medication
- Intensity of event

- Onset date and time
 - a) When assessing relationship to study medication, relationship as reported by the investigator, events will be reported as related or not to study medication. Related events will take precedence over unrelated events in determining the event to include in summary tables.
 - b) More intense events will take precedence over less intense events in determining the event to include in summary tables.
 - c) Earlier onset date-time events will take precedence over late onset date-time events in determining the onset to include in summary tables.

When reporting adverse events by intensity, in addition to providing a summary table based on the event selection criteria detailed above, summary tables will also be provided based on the most intense event during the analysis period - independent of relationship to study medication. For these tables, the following criteria, in order of precedence, will be used to select the event to be included in summary tables:

- Intensity of event
- Onset date and time

6.7.2 At event level

At event level, each unique AE record will be counted. Unique AE record can be obtained by collapsing all AE records following a standard algorithm. In addition to frequency summary, exposure adjusted summary will also be provided where the overall exposure of a subject is calculated from first dose day to the last day of short-term treatment regardless of whether a subject has had an event or not.

6.8 Fasting state

Lipids parameters listed in the protocol include TG, LDL-C, HDL-C, total-C and FFA. For TG, calculated LDL-C and FFA, only data collected in fasting state will be used for analysis. For direct LDL-C, HDL-C and total-C, data collected in both fasting and non-fasting state will be used for analysis.

For FPG and fasting C-peptide, only assessments documented with the subject in fasting state will be summarized and listed.

6.9 Percent compliance calculation

Percent compliance for the double-blind study medication during the double-blind treatment period is defined for each subject as the number of tablets taken, divided by the number of tablets that should have been taken.

The number of tablets that should have been taken is calculated as 1 + the number of days from the first double-blind treatment period dose recorded in the “Record of Study Medication” to the last double-blind treatment dose, times the prescribed daily dose (i.e. 2 tablets per day, one from each bottle). The number of tablets taken is the total number of tablets recorded (sum of bottle 1 and bottle 2) as taken based on the CRF, summed over the

days counted when calculating the number of tablets that should have been taken, including the day of the last double-blind treatment dose.

6.10 Strip sign for selected laboratory data

For selected laboratory test values that have been received with an operator sign as a part of the result ($>$, \geq , $<$, or \leq), a process to strip the operator sign will be applied and the resulting numeric values will be used for data analysis. The raw value with operator will remain as such on the CRF (or in the electronic record) and in the database.

The applicable impacted laboratory tests and applicable operator signs will be identified during the course of the study and study monitoring. For laboratory parameters not included in any statistical analyses, operator signs will not be stripped and the value will counted as missing.

6.11 United States Conventional Units and Standard International Units for Laboratory Data

Unless otherwise specified, all analyses of laboratory data (independently of being safety or efficacy) will be performed in both United States Conventional Units (US) and Standard International Units (SI). Conversion between US and SI, and vice versa, will be performed using the BMS standard conversion factors.

Analysis of HbA1c and CrCl (Cockcroft and Gault) will be performed only in United States Conventional Units as these units are accepted by Health Authorities in other countries.

6.12 Capillary glucose readings of plasma glucose values and whole blood glucose values

Capillary Glucose reading values in plasma are typically about 12% higher than readings based on whole blood. When necessary, the capillary whole blood glucose reading values will be converted to capillary plasma equivalent glucose reading values by multiplying them with the conversion factor of 1.12. Respectively, when necessary, the capillary plasma glucose reading values will be converted to capillary whole blood glucose reading equivalent values by dividing them with the same conversion factor.

6.13 Laboratory evaluations

All laboratory evaluations performed by central laboratories and local laboratories that are included in the database will be included in summary tables and in the listings.

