- low-density lipoprotein cholesterol
- high-density lipoprotein cholesterol
- total cholesterol
- free fatty acid
- uric acid

Additional laboratory data summaries

A 24-week short-term double-blind treatment period, the following summaries will be provided.

Shift Tables for Electrolytes (Sodium, Potassium, Calcium, Phosphate, and Magnesium) Categories

Shift tables of Treated Subjects Data Set subjects with electrolytes values in categories of low, normal, and high (based on normal range of central laboratory) will be summarized by treatment group using the highest (for sodium, calcium, phosphate, and magnesium) and lowest (for sodium, potassium, and calcium) values (regardless of post-randomization insulin up-titration) obtained during the short-term double-blind treatment period.

Shift Tables for Urine Albumin Excretion Categories

Shift tables of Treated Subjects Data Set subjects with urine albumin to creatinine ratios in 0 - < 30mg/g (normoalbuminuria), 30 - < 300mg/g (microalbuminuria), and ≥ 300 mg/g (macroalbuminuria) will be summarized by treatment group using the Week 24 values (the last observation regardless of post-randomization insulin up-titration prior to Week 24 will be used if no Week 24 measurement is available).

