6.3 Longitudinal assessments

Day 1 for the short-term double-blind treatment period is the start date of double-blind treatment medication. The observation closest to the target day (and time where applicable) is the measurement used in the analysis for each scheduled visit.

The following visit window will apply for all laboratory parameters, vital signs and physical measurements in the short-term double-blind treatment period up to 24 weeks.

Table 9 Visit Windows for Short-term Double-blind Treatment Period Up to Week 24

Visit	Target Day	Day Range
Week 1	8	Post-baseline -11*
Week 2	15	12-22*
Week 4	29	23-43*
Week 8	57	44-71*
Week 12	85	72-106*
Week 18	127	107-148*

Table 9 Visit Windows for Short-term Double-blind Treatment Period Up to Week 24

Visit	Target Day	Day Range
Week 24	169	149 - Last day of double-blind treatment + 8 day for HbA1c, body weight, BMI, patient reported outcomes or 149 - Last day of double-blind treatment +1 day for insulin dose, CGM parameters, FPG, SMBG

* on or before the last day of double-blind treatment.

Table 10 Visit Windows for Short-term Double-blind Treatment Period Up to Week 24 for CGM parameters, Total daily Insulin and 6-point SMBG

Visit	Target Day	Day Range
Week 2	15	1-40*
Week 12	85	60-110*
Week 24	169	140- Last day of double-blind treatment

* on or before the last day of double-blind treatment.

The use of post double-blind treatment observations is specified in Section 6.4.

For all safety laboratory parameters, the use of post-double-blind treatment observations is specified in Section 4.2.4.5.

For laboratory and non-laboratory parameters, if a subject has more than one measurement included within a window, the assessment closest to the target day will be used. In case of ties between observations located on different sides of the target day, the earlier assessment will be used. In case of ties located on the same side of the target day (i.e. more than one value for the same day but different time), the value with the earlier entry date/time will be used.

For measurements referring to 24-hour collection periods (i.e. daily insulin dose) and those referring to multiple data collection points over multiple days (i.e. 6-point measurement parameters and CGM parameters) more than one value will be included in the analysis window. The value for analysis for the visit window will be calculated as the daily average of all available values for analysis for each parameter falling in the analysis window.

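### Section 6.13 pools local and central laboratory results, but the visit-window rule sets no source priority and the electrolyte shift tables grade every value by the central laboratory's range

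*SAP*

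**What the plan says.** Section 6.13 admits results from both sources without exception by parameter, visit or table: "All laboratory evaluations performed by central laboratories and local laboratories that are included in the database will be included in summary tables".

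Section 6.3 then decides which value represents a visit. Its scope is wide: "The following visit window will apply for all laboratory parameters, vital signs and physical measurements". Its selection rule has three steps:

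- Main rule: "if a subject has more than one measurement included within a window, the assessment closest to the target day will be used".
- Tie on opposite sides of the target day: "In case of ties between observations located on different sides of the target day, the earlier assessment will be used".
- Tie on the same day: "the value with the earlier entry date/time will be used".

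None of these steps refers to the laboratory that issued the result.

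Section 4.2.4.5 builds the electrolyte shift tables differently. They use each subject's highest value (sodium, calcium, phosphate, magnesium) or lowest value (sodium, potassium, calcium) over the short-term period, and place subjects "in categories of low, normal, and high (based on normal range of central laboratory"). Local values are not excluded.

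Appendix 9.3 grades marked abnormalities by fixed limits, by multiples of ULN, or by change from the pre-treatment value. Where ULN is used, the SAP does not say whose ULN it is.

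**The concern.** Two laboratories can differ in assay, calibration and reference range. If a local value stands in for a central one at a visit, the change from baseline may compare two assays within one subject. If a local value is the extreme that enters a shift table, it is labelled low, normal or high by limits that were not set for the assay that produced it.

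The first problem adds noise to by-visit laboratory summaries. The second can put a subject in the wrong category of a safety table. Both follow from applying the rules as written, and a programmer has no text that would justify doing otherwise.

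**Working it through.** No figure in the SAP is tied to this point, so the check is mainly to run the stated rules.

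**1. Is there a source rule elsewhere?** Section 6.2 sends repeat results on a sample with the same collection date and time to a sponsor standard that is not shown. That does not cover separate local and central draws. The baseline definition in section 4.1.2.1 (last assessment up to first dose) has no source preference either.

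**2. The section 6.3 rule at Week 24 (target day 169):**

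- Central day 171, local day 169: the local value is used, because it is closer.
- Central day 171, local day 167: tie at 2 days; the local value is used, because it is earlier.
- Both on day 169, local drawn first: the local value is used.
- Central day 169, local on any other day: the central value is used.

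In general, if the central draw is *k* days late, a local draw replaces it on 2*k* − 1 closer days plus 1 tie day, that is 2*k* days, provided the window is wide enough. For *k* = 2, 3 and 5 this gives 4, 6 and 10 days. Those are the counts in each of the Week 4, 8, 12 and 18 windows.

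**3. The electrolyte shift tables.** Here the visit window plays no part. The extreme of all values in the period is taken, and under section 6.13 local values are among them. The only range named is the central laboratory's. A local extreme is therefore graded by another laboratory's limits.

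**4. How much could that misgrade?** The SAP gives no assay data, so this is an assumption. Let the central range be mean ± 1.96 SD and let the local assay read *s* SD higher. The share of single results from normal subjects classed as high is 1 − Φ(1.96 − *s*):

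- *s* = 0: 2.5%
- *s* = 0.25: 4.4%
- *s* = 0.5: 7.2%
- *s* = 1: 16.9%

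**5. Scale for HbA1c, if any local HbA1c existed.** Section 1.3 gives 243 per arm, SD 1.1%, difference 0.35% and two-sided alpha 0.0262. The standard error of the difference is 1.1 × √(2/243) = 0.0998. Then 0.35/0.0998 = 3.507, the critical value is 2.223, and Φ(3.507 − 2.223) = 0.900, which reproduces the stated 90% power. Assume 2% of one arm carries a local value offset by 0.25%. The arm mean shifts by 0.02 × 0.25% = 0.005%. That is 0.005/0.0998 ≈ 0.05 standard errors, or 0.005/0.35 ≈ 1.4% of the target difference.

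**The case against.** The best defence is that including every result is a sound, inclusive convention for safety data, and that the details of which assays are central belong to the protocol. Part of this stands: dropping local results from the shift tables would remove real extremes from tables meant to show them. It does not answer the grading problem, because the SAP itself names the central range.

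A reader might infer more than the document supports:

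- **That all local results are graded by the central range.** This is stated only for the electrolyte shift tables. The urine albumin categories and many marked-abnormality limits are fixed cut-offs, and for ULN-based criteria the SAP is silent.
- **That displacement and misgrading occur together.** They act in different tables: the first in by-visit summaries, the second in tables of extremes.
- **That the HbA1c result is at risk.** Section 6.11 refers to "all analyses of laboratory data (independently of being safety or efficacy"), but it is a rule about units. Nothing shows that local HbA1c or FPG is collected. Where a laboratory is named for HbA1c (Table 1, item 1; Appendix 9.1, item 4), it is the central one. Setting one subject's assay offset against the 0.35% between-arm difference would also mislead, since the two are not on the same footing.
- **That the arms would be biased.** This would need local testing to differ by arm. It is plausible if acute events such as ketoacidosis prompt local tests, but the SAP gives no data on it.

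**Conclusion.** The point holds as a narrow but real defect. Section 6.13 pools the two sources, section 6.3 then lets a local value replace a central one at the same visit, and section 4.2.4.5 grades local electrolyte extremes by the central range. Replacement is not automatic: a central draw on the target day is safe from a local draw on any other day.

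The size cannot be stated, because the number of local results, their assay offsets and their ranges are not given. The 4.4% to 16.9% figures rest on assumed offsets of 0.25 to 1 SD. For HbA1c the effect is likely negligible, about 0.05 standard errors under assumptions that place all affected subjects in one arm with offsets in the same direction. The electrolyte shift tables carry most of the exposure. The correction is cheap and worth making before unblinding; it does not affect the sample size or the primary model.

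**What to change.** Amend three places.

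- **Sections 6.3 and 6.13:** when a window holds both a central and a local result, the central result is used for by-visit change-from-baseline summaries, and for HbA1c and FPG if any local values exist. A local result is used only when no central one is available. The same preference should apply to the baseline value.
- **Section 4.2.4.5, electrolyte shift tables:** keep local values, but classify each result by the issuing laboratory's own normal range. Do this before choosing the worst category, since the numerically highest or lowest value need not be the one furthest outside its own range.
- **Appendix 9.3:** apply the issuing laboratory's ULN to the ULN-based marked-abnormality and liver criteria.

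The cost is SAP wording and a small programming change. Local reference ranges must be held in the database, and a local value without a range could only be listed in place of being graded. No visit becomes missing, because local values still serve where no central one exists.

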7. CHANGES OF ANALYSIS FROM PROTOCOL

- 1) Self-monitored blood ketones that are not associated with an event sent for DKA adjudication will be analysed.

9. APPENDIX

9.1 List of significant protocol deviations

Number	Significant Deviation
1	Randomized subjects with no signed and dated written informed consent.
2	Randomized subjects without a diagnosis of T1DM defined as central laboratory test of C-peptide < 0.7 ng/ml.
3	Re-enrolled randomized subjects who have discontinued the study as a screen or lead-in failure
4	Randomized with a screening visit central laboratory HbA1c < 7.7% or > 11%.
5	Randomized subjects with BMI < 18.5 kg/m ² .
6	Randomized subjects with age < 18 or > 75 years of age.
7	Randomized subjects (women) without a negative serum or urine pregnancy test (minimum sensitivity 25 IU/L or equivalent units of HCG) within 24 hours prior to the start of investigational product.
8	Randomized subjects (women) who are breastfeeding.
9	Randomized subjects (women) of child bearing potential who are unwilling or unable to use an acceptable method to avoid pregnancy for the entire study period.
10	Randomized subjects with history of T2DM, maturity onset diabetes of young (MODY), pancreatic surgery or chronic pancreatitis.
11	Randomized subjects with previous use of dapagliflozin and/or any other SGLT-2 inhibitors
12	Randomized subjects with any use of metformin and/or thiazolidinediones within 2 months prior to the Screening visit.
13	Randomized subjects with any use of any non-insulin antihyperglycemic agent within 1 month prior to the screening visit.
14	Randomized subjects with history of diabetic ketoacidosis (DKA) requiring medical intervention (eg, emergency room visit and/or hospitalization) within 1 month prior to the screening visit.
15	Randomized subjects with history of hospital admission for glycemic control (either hyperglycemia or hypoglycemia) within 1 month prior to the screening visit.
16	Randomized subjects with protocol defined frequent episodes of severe hypoglycemia within 1 month prior to the screening visit.
17	Randomized subjects with symptoms of poorly controlled diabetes, including marked polyuria and polydipsia with >10% weight loss during the three months prior to screening, or other signs and symptoms.
18	Randomized subjects with history of Addison's disease or chronic adrenal insufficiency.
19	Randomized subjects with history of diabetes insipidus.
20	Randomized subjects with myocardial infarction within 6 months of the enrollment visit.

Number	Significant Deviation
21	Randomized subjects with cardiac surgery or revascularization (coronary artery bypass surgery /percutaneous transluminal coronary angioplasty) within 6 months of the enrollment visit.
22	Randomized subjects with Unstable angina within 6 months of the enrollment visit.
23	Randomized subjects with Unstable congestive heart failure (CHF) within 6 months of the enrollment visit.
24	Randomized subjects with CHF New York Heart Association (NYHA) Class III or IV within 6 months of the enrollment visit.
25	Randomized subjects with transient ischemic attack (TIA) or significant cerebrovascular disease within 6 months of the enrollment visit.
26	Randomized subjects with unstable or previously undiagnosed arrhythmia within 6 months of the enrollment visit.
27	Randomized subjects with history of unstable or rapidly progressing renal disease
28	Randomized subjects with history of congenital renal glucosuria
29	Randomized subjects with history of renal allograft
30	Randomized subjects with significant protocol defined hepatic diseases.
31	Randomized subjects with known immunocompromised status.
32	Randomized subjects with donation of blood, blood products to a blood bank, blood transfusion, or participation in a clinical study requiring withdrawal of > 400 mL of blood > 8 wks prior screening
33	Randomized subjects with malignancy within 5 years of the screening visit (with the exception of treated basal cell or treated squamous cell carcinoma)
34	Randomized subjects with history of bladder cancer
35	Randomized subjects with history of radiation therapy to the lower abdomen or pelvis at any time
36	Randomized subjects with aspartate aminotransferase (AST) > 3X upper limit of normal.
37	Randomized subjects with alanine aminotransferase (ALT) > 3X ULN.
38	Randomized subjects with serum total bilirubin (TB) > 2.0x ULN.
39	Randomized subjects with Calculated Creatinine Clearance <60 ml/min/1.73m ² .
40	Randomized subjects with hemoglobin ≤ 11.0 g/dL (110 g/L) for men; hemoglobin ≤ 10.0 g/dL (100 g/L) for women.
41	Randomized subjects with positive for hepatitis B surface antigen or anti-hepatitis C virus antibody.
42	Randomized subjects with allergies or contraindication to the contents of dapagliflozin tablets or insulin.
43	Randomized subjects (women) who are pregnant.
44	Randomized subjects who are prisoners or are involuntarily incarcerated.
45	Randomized subjects with subjects who are compulsorily detained for treatment of either a psychiatric or physical (e.g., infectious disease) illness.

Number	Significant Deviation
46	Randomized subjects on a commercial weight loss program with ongoing weight loss, or on an intensive exercise program.
47	Randomized subjects who history of bariatric surgery or lap-band procedure within 12 months prior to screening.
48	Randomized subjects with replacement or chronic systemic corticosteroid therapy, defined as any dose of systemic corticosteroid taken for > 4 weeks within 3 months prior to the Day 1 visit.
49	Randomized subjects with any unstable endocrine, psychiatric or rheumatic disorders as judged by the Investigator.
50	Randomized subjects who are volume depleted or at risk for volume depletion due to co-existing conditions or concomitant medications and cannot carefully monitor their volume status.
51	Randomized subjects who are, in judgment of Investigator, unlikely to comply with protocol, or to correctly self administer MDI and/or insulin pump, or with severe medical or psychological condition.
52	Randomized subjects with any condition which, in the judgment of the Investigator, may render the subject unable to complete the study or which may pose a significant risk to the subject.
53	Randomized subjects who are currently abusing alcohol or other drugs or have done so within the last 6 months prior to the Day 1 visit.
54	Randomized subjects who are a participating investigator, study coordinator, employee of an investigator or immediate family member of any of the aforementioned.
55	Randomized subjects who are employee of BMS, AstraZeneca (AZ), or their relatives.
56	Randomized subjects administrated of any other investigational drug within 30 days of the screening visit.
57	Randomized subjects with clinical conditions, clinically significant abnormalities, after screening and prior to randomization which, in the Investigator's judgment, should preclude treatment.
58	Randomized Subjects that used antihyperglycemic medication (other than protocol allowed medication and study medication) for any duration during short-term double-blind treatment-period.
59	Randomized subjects administered any weight loss medication.
60	Randomized subjects administered acetaminophen (paracetamol) containing medications while using the Dexcom CGM device, and 24 hours prior to insertion.
61	Randomized subjects not discontinued from treatment period despite withdrawal of informed consent.
62	Randomized subjects not discontinued from treatment despite adverse event, laboratory abnormality, intercurrent illness where study continuation is not in the best interest of subject per Investigator
63	Randomized subjects not discontinued from treatment despite unblinding a subject for any reason (emergency or non-emergency)

Number	Significant Deviation
64	Randomized subjects not discontinued from treatment period despite pregnancy.
65	Randomized subjects not discontinued from treatment period despite termination of the study by the Sponsor.
66	Randomized subjects not discontinued from treatment period despite loss of ability to freely provide consent through imprisonment or involuntary incarceration for treatment of illness.
67	Randomized subjects not discontinued from treatment period despite Creatinine Clearance < 30 ml/min.
68	Randomized subjects not discontinued from treatment period despite at least one protocol-defined hypoglycemia episode that leads to a loss of consciousness and/or seizure as determined by Investigator
69	Randomized subjects not discontinued from treatment period despite change of insulin administration method (eg, switch from MDI to CSII or vice versa).
70	Randomized subjects not discontinued from treatment period despite initial and repeat central laboratory tests meet protocol defined criteria for ALT, AST, TB.
71	Randomized subjects administered study medication from an incorrect kit number (dispensing error).
72	Randomized subjects use of any GLP-1 receptor agonist within the protocol specified time frame prior to the screening visit.

The above significant protocol deviations will be listed in a separate report.

